7.5.2 Clinical Laboratory Evaluation

The baseline visit is the last measurement taken prior to initial study drug administration.

Quantitative clinical laboratory variables, i.e., hematology and biochemistry based on central assessment will be summarized using mean, standard deviation, minimum, maximum and median for each treatment group at each visit. Additionally, a within-subject change will be calculated as the post-baseline measurement minus the baseline measurement and summarized in the same way. Each laboratory result will be classified as low (L), normal (N), or high (H) at each visit according to the laboratory supplied reference ranges.

The number and percentage of subjects below and above reference range will be summarized for each treatment group at each visit.

Laboratory results will also be graded using NCI-CTCAE, where possible. Parameters that have criteria available for both low and high values, i.e., hypo- and hyper-, will be summarized for both criteria. The same subject can be counted for both values if the subject has different laboratory values meeting each criterion. The number and percentage of subjects with grade 3 or 4 laboratory test result will be summarized by treatment group and laboratory parameter (the name of the adverse event associated with the abnormal laboratory test result will be presented).

Laboratory results based on local assessment and bone marrow results will be listed only.

7.5.2.1 Liver Enzymes and Total Bilirubin

The following potentially clinically significant criteria in liver function tests for Alkaline Phosphatase (ALP), Alanine Transaminase (ALT), total bilirubin, Aspartate Transaminase (AST) and their combination are defined. The subject's highest value during the investigational period will be used.

Parameter ALT	Criteria > 3xULN > 5xULN > 10xULN > 20xULN
AST	> 3xULN > 5xULN > 10xULN > 20xULN
ALT or AST	> 3xULN
Total Bilirubin	> 2xULN
ALP	> 1.5xULN
ALT and/or AST AND Total Bilirubin(*)	(ALT and/or AST > 3xULN) and total bilirubin > 2xULN

^(*) Combination of values measured within same sample

The number and percentage of subjects with potentially clinically significant values in liver enzymes and total bilirubin during the investigational period will be presented by treatment group.

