- c. Includes medications taken within 28 days prior to cycle 1 day 1.
- d. Woman of childbearing potential must have a negative serum or urine pregnancy test (minimum sensitivity 25 IU/L or equivalent units of human chorionic gonadotropin) within 72 hours prior to the start of study treatment.
- e. Screening ECG is required. ECG assessment will be evaluated at predose of cycle 1 day 1, cycle 1 day 8, cycle 1 day 15 and day 1 of each subsequent cycle. Predose assessments should be taken within 1 hour before drug administration. The 12-lead ECGs will be recorded in triplicate (3 separate ECGs 10 minutes resting prior to first ECG and at least 5 minutes apart per time point) and transmitted electronically for central reading. The mean QTcF of the triplicate ECG tracings based on central reading will be used for final treatment decisions and AE reporting. If the mean of the triplicate QTcF is > 500 ms at any time point (by either value on ECG tracing printout or central reading), then triplicate ECGs will be repeated (within 2 hours if based on value on ECG tracing printout and as soon as possible if based on central reading). If the repeat ECG confirms a mean of the triplicate QTcF > 500 ms, dosing of ASP2215 will be interrupted for up to 14 days. While ASP2215 may be interrupted temporarily based on value on ECG tracing printout, the central reading should be used for final treatment decisions. Cardiology consult will be obtained as medically indicated. If QTcF resolves to ≤ 480 ms (grade 1 or less) by central reading within 14 days, the subject may resume dosing at the reduced dose.
- f. Urinalysis only required at screening. Uric acid will be tested on days 1, 4, 8 and 15 in cycle 1. Additional laboratory tests should be performed according to institutional standard of care.
- g. Subjects may be screened and randomized from local labs only. However, samples must also be submitted for central read. Labs and/or ECG can be repeated during screening period.
- h. MUGA scans or ECHO (per standard of care) are to be performed at screening for subjects with history of congestive heart failure New York Heart Association Class 3 or 4 (unless MUGA scans or ECHO performed either within 1 month prior revealed left ventricular ejection fraction ≥ 45%).

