- e. For subjects who plan to proceed to HSCT and resume ASP2215 treatment after HSCT, AE collection will continue until the start of the HSCT conditioning regimen and AE collection will resume upon the resumption of ASP2215 treatment until 30 days after the last dose of study drug. For subjects who do not plan to resume ASP2215 treatment after HSCT, AE collection will continue until the start of the HSCT conditioning regimen or 30 days after the last dose of study drug, whichever comes first. However, the following AE/SAEs will continue to be collected until 30 days after the last dose of study drug, regardless of the time of the HSCT conditioning regimen:
 - Any study drug related AE that is ongoing will be followed until resolved
 - Any SAE that is deemed to be related to study drug by the investigator
 - Any event of veno-occlusive disease (VOD) of the liver, cardiac failure, Grade 3 or higher QT prolongation, rhabdomyolysis, drug-induced liver injury, or PRES
 - Adverse events leading to death
- f. Telephone contact with the subject is sufficient unless any assessment must be repeated for resolution of treatment-related AEs.
- g. Only SAE data that is related to ASP2215 will be collected.
- h. Telephone contact every 3 months. Ad hoc contact will be required during interim analysis.
- i. Includes Brief Fatigue Inventory, Functional Assessment of Chronic Illness Therapy—Dyspnea-Short Forms, Functional Assessment of Cancer Therapy—Leukemia and dizziness and mouth sores items. The BFI will be administered at pre-HSCT/end of treatment visit. Functional Assessment of Cancer Therapy—Dyspnea-Short Forms, Functional Assessment of Cancer Therapy—Leukemia and dizziness and mouth sores items will be administered at pre-HSCT/end of treatment visit.
- j. Ophthalmologic assessment to be performed by visual acuity measurement and ophthalmoscopy, at the Pre-HSCT/end of treatment (+/- 7 days). In symptomatic subjects, the ophthalmologic assessment should also include slit lamp biomicroscopy, visual fields and optical coherence tomography (OCT).
- k. If possible, patient reported outcome measures should be performed prior to any other assessments on that visit day.

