3.2 Study Design

3.2.1 Study Design

This is a phase 3, open-label, multicenter, randomized study to compare the efficacy and safety of ASP2215 therapy to salvage chemotherapy in FLT3-mutated AML subjects who are refractory to or have relapsed after first-line AML therapy. Approximately 140 centers in North America, Europe, Asia and rest of the world will participate in this study.

Three hundred sixty nine subjects will be randomized. The randomization of the 369 subjects will be in a 2:1 ratio to receive ASP2215 or salvage chemotherapy. Subjects will enter the screening period up to 14 days prior to the start of treatment. Prior to randomization, the Investigator will preselect a salvage chemotherapy regimen for each subject; options will include LoDAC, azacitidine, MEC or FLAG-IDA. The randomization will be stratified by response to first-line therapy and preselected salvage chemotherapy. Subjects will be administered treatment over continuous 28-day cycles and per institutional guidelines for chemotherapy product preparation and administration. The dose and duration of study treatments are outlined in Section 5.1.1 of the protocol.

For subjects taking ASP2215, LoDAC or azacitidine, treatment should continue until the subject meets a treatment discontinuation criterion.

Subjects receiving MEC or FLAG-IDA will receive 1 cycle of therapy and will be assessed for response on or after day 15, per institutional guidelines. If the bone marrow cellularity is

20% or greater with at least a 50% reduction in blasts, the subject may receive a second cycle of the same chemotherapy. If bone marrow cellularity is between 5% and 20%, the investigator should make the decision whether the subject should receive another treatment cycle or be observed for recovery. If bone marrow cellularity is 5% or less, the subject will be observed for recovery. Subjects achieving CR, CRi or CRp may receive a second cycle of chemotherapy at the Investigator's discretion. Subjects with no response (NR) or progressive disease following cycle 1 will discontinue study treatment.

Dose adjustments for ASP2215 are described in Section 5.1.2 of the protocol.

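### The combined ALT/AST and bilirubin row needs both values in one central sample, so a subject crossing the two thresholds in different samples is never counted as a combined case

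*SAP*

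**What the plan says.** Section 7.5.2.1 lists potentially clinically significant liver criteria. For the criteria in general it states: "The subject's highest value during the investigational period will be used". The combined row (ALT and/or AST above 3×ULN together with total bilirubin above 2×ULN) carries a footnote that replaces this with a stricter rule: "Combination of values measured within same sample".

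Section 7.5.2.1 does not name the source of the values. Its parent, Section 7.5.2, does: "hematology and biochemistry based on central assessment will be summarized", and "Laboratory results based on local assessment and bone marrow results will be listed only".

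Tables 1 and 2 in Section 2 schedule chemistry on the same days in both arms: cycle 1 days 1, 4, 8 and 15, cycle 2 days 1 and 15, then day 1 of each later cycle. Section 3.2.1 fixes the cycle length: "Subjects will be administered treatment over continuous 28-day cycles". Table 3 adds one chemistry sample at the pre-HSCT/end of treatment visit and none at the 30-day follow-up. On further testing, the footnotes to Tables 1 and 2 say only: "Additional laboratory tests should be performed according to institutional standard of care".

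**The concern.** The single-parameter rows take the worst value at any time, while the combined row takes only coincident values. A subject with ALT above 3×ULN in one sample and bilirubin above 2×ULN in the next appears in two separate rows but not in the row that joins them. This needs no particular clinical pattern, only that the two thresholds are crossed in different samples.

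Nothing else in the SAP gives a joint count. The grade 3 or 4 summary in Section 7.5.2 is by parameter. The liver entry in Appendix 3 searches reported adverse event terms and does not link laboratory values.

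The end-of-study analysis covers safety data only (Sections 1 and 3.2.1), so a count of possible liver injury that runs low would stand without other laboratory evidence in table form. Table 3 footnote e names the topic among the events collected regardless of conditioning for transplant: "drug-induced liver injury, or PRES".

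**Working it through.** The SAP gives no figure on this point, so there is none to reproduce. The check rebuilds the sampling days and asks which pairs of rises can be counted.

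**Sampling days.** With 28-day cycles, the scheduled study days are 1, 4, 8, 15, 29, 43, 57, 85, 113 and so on. The gaps are 3, 4, 7, 14, 14 and 14 days up to cycle 3 day 1 (day 57), and 28 days after that.

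**Same-sample rule, no overlap.** If bilirubin rises above its threshold only after ALT/AST has fallen below its own, no sample can contain both. Capture is 0% at any spacing.

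**Same-sample rule, with overlap.** For a constant gap g and an overlap of w days, P(a scheduled sample falls in the overlap) = min(1, w/g).

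| Overlap | g = 7 | g = 14 | g = 28 |
|---|---|---|---|
| 7 days | 100% | 50% | 25% |
| 14 days | 100% | 100% | 50% |
| 21 days | 100% | 100% | 75% |
| 28 days | 100% | 100% | 100% |

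**What relaxing the rule recovers.** Both rises are assumed to last d days, with bilirubin lagging by half of d or by all of d. Onset of the ALT/AST rise is uniform within each period (60,000 simulated onsets), and sampling is on the nominal days. Each cell gives capture under the same-sample rule → capture when the two values may come from different samples.

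| d | Lag | Onset days 1–15 | Onset days 15–43 | Onset day 57 on |
|---|---|---|---|---|
| 7 | 3.5 | 50% → 75% | 25% → 25% | 12% → 12% |
| 7 | 7 | 0% → 50% | 0% → 0% | 0% → 0% |
| 14 | 7 | 50% → 100% | 50% → 100% | 25% → 25% |
| 14 | 14 | 0% → 100% | 0% → 100% | 0% → 0% |
| 21 | 10.5 | 75% → 100% | 75% → 100% | 38% → 50% |
| 21 | 21 | 0% → 100% | 0% → 75% | 0% → 50% |
| 28 | 14 | 100% → 100% | 100% → 100% | 50% → 100% |
| 28 | 28 | 0% → 100% | 0% → 100% | 0% → 100% |

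The last column can be checked by hand. For back-to-back rises on a 28-day grid, both are sampled with probability max(0, (2d − 28)/28) for d up to 28. This gives 0 for d ≤ 14, 14/28 = 50% for d = 21, and 28/28 = 100% for d = 28.

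**Length of the window.** Day 1 visits from cycle 2 on carry ±2 days, so two consecutive visits can be 28 + 2 + 2 = 32 days apart. A 30-day window would not always span them.

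**The case against.** The strongest reply is that the same-sample rule is clear and prespecified. The footnote expressly qualifies the highest-value sentence, so there is no contradiction. The row is descriptive, with no test or decision attached, and rule and schedule are the same in both arms. Subjects with separated rises who are sampled centrally still enter the ALT, AST and bilirubin rows. Liver events reported as adverse events, whichever laboratory found them, enter the tables of Section 7.5.1 and the Appendix 3 search. The drug-induced liver injury text in Table 3 concerns adverse event collection and feeds those tables, not the laboratory table. All of this stands and limits the weight of the point, but none of it supplies a joint count.

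A reader might infer four stronger things that the SAP does not support:

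- **That central samples are 28 days apart throughout.** This holds only after cycle 3 day 1.
- **That wide spacing is why non-overlapping rises are missed.** The rule misses all of them at any spacing. Spacing governs how many short overlapping rises are missed and what a wider rule could recover.
- **That every between-visit or in-hospital test is local, so that the worst values never reach the tables.** The SAP says only that extra tests follow institutional practice, and a peak in a central sample is tabulated.
- **That the comparison between arms is distorted.** MEC and FLAG-IDA run for at most two cycles, so the 28-day grid mainly concerns the continuing treatments. The SAP gives no basis for the size or direction of any effect.

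**Conclusion.** The point holds as a minor one. The combined row can undercount because it requires one central sample. It captures 0% of non-overlapping pairs at any interval. After cycle 3 day 1 it captures about overlap/28 of overlapping pairs on scheduled samples.

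Those percentages rest on assumed durations and lags. The SAP gives neither, so the number of subjects affected cannot be estimated. The overlap/28 figure also reflects the visit schedule as much as the rule. What the rule alone costs is the difference between the paired figures in the second table, which is largest in the densely sampled first two cycles. That only central values feed Section 7.5.2.1 is read from its parent section. The end of treatment sample and any unscheduled central samples would raise capture somewhat and are not modelled. The efficacy conclusions are unaffected.

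**What to change.** In Section 7.5.2.1:

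1. Keep the same-sample row.
2. Add a row counting subjects whose total bilirubin above 2×ULN falls on the same day as, or within a stated number of days after, ALT or AST above 3×ULN. Set the window to span two consecutive scheduled visits, that is, at least 32 days.
3. Add a supplementary, flagged row repeating that count with local and unscheduled values, judged against the reporting laboratory's ULN where available, and mark subjects who qualify only through local values. This is needed because from cycle 3 on the window alone recovers no back-to-back rises of 14 days or less. Keeping it separate avoids mixing sources in the main rows.
4. State which source each row uses. By-visit means can stay central only.

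The cost is a few lines of SAP text and some table programming. A longer window will admit some non-specific cases, which is why the same-sample row should stay beside it. The third row depends on local reference limits being in the database, which the SAP does not confirm. Using local values is not foreign to the plan: Section 6.1.3.3 already fills missing central hematology with local results when deriving response.

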7.5.3 Vital Signs

The baseline visit is the last measurement taken prior to initial study drug administration.

Vital signs (systolic blood pressure, diastolic blood pressure, pulse rate, and body temperature) will be summarized using mean, standard deviation, minimum, maximum and median by treatment group and visit. Additionally, a within-subject change will be calculated per visit as the post-baseline measurement minus the baseline measurement and summarized by treatment group and visit.

Tables for potentially clinically significant vital signs will be generated using baseline value and highest value obtained during treatment for each subject for each treatment group.

The following potentially clinically significant criteria are defined for each parameter:

Vital Sign Variable	Criteria
SBP	≥180 mmHg AND ≥20 mmHg change from baseline
DBP	≥105 mmHg AND ≥15 mmHg change from baseline
Pulse Rate	≥120 bpm AND ≥15 bpm change from baseline

7.5.4 Electrocardiograms (ECGs)

12-lead ECGs will be recorded in triplicate at the scheduled time points. Each ECG tracing will be taken 5 minutes apart. ECGs will be read at the site for clinical decision making and transmitted to a central reviewer. Data from the central reviewer will be used in summary presentations. The three values of each ECG parameter within a time point from the central reviewer will be averaged to determine time-specific parameter for a subject, and used in summaries.

The QT interval corrected for heart rate by Fridericia's formula, QTcF, is defined as: $QTc(F) = QT/(RR)^{0.33}$, where RR interval is inversely proportional to heart rate (approximately RR = 60/heart rate).

The QTcF interval will be summarized using frequency tables for each treatment group at each treatment visit and time point for values of clinical importance using the range criteria below.

	QTc Interval Criteria Value (msec)	
	Interval Category	
Normal	≤ 450	
Borderline	$> 450 \text{ to } \le 480$	
Prolonged	$> 480 \text{ to} \le 500$	
Clinically significant	> 500	

Number and percent of subjects with maximum postbaseline QTcF > 480 msec and the time to maximum post baseline QTcF value > 480 msec will be summarized by treatment group.

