- q. Includes Brief Fatigue Inventory, Functional Assessment of Chronic Illness Therapy–Dyspnea-Short Forms, Functional Assessment of Cancer Therapy-Leukemia and dizziness and mouth sores items. The BFI will be administered at cycle 1 day 1 predose, cycle 1 day 8 (± 1 day), day 15(± 1 day), cycle 2 day 1 (± 2 days), day 15(± 1 day) and all subsequent cycles day 1 (± 2 days). Functional Assessment of Chronic Illness Therapy–Dyspnea-Short Forms, Functional Assessment of Cancer Therapy-Leukemia and dizziness and mouth sores items will be administered at cycle 1 day 1 predose, cycle 2 day 1 (± 2 days) and all subsequent cycles day 1 (± 2 days).
- r. If possible, patient reported outcome measures should be performed prior to any other assessments on that visit day.
- s. A cycle 1 day 8 ECG will be taken and the central read results will be provided to the site 24 hours after receipt of the tracing. A confirmatory ECG should be performed on cycle 1 day 9 if the mean QTcF from cycle 1 day 1 to cycle 1 day 8 has increased > 30 ms with no other known etiology, based on the central read ECG. On cycle 1 day 8, it is recommended that the ECG is taken as early as possible in the morning and transmitted immediately. In addition, it is recommended that the cycle 1 day 9 visit is scheduled later in the day in order to allow for receipt and assessment of the cycle 1 day 8 central read ECG. This also allows for a subject to be contacted if the cycle 1 day 9 ECG is no longer required. If the cycle 1 day 9 ECG is still required, the result of the central read ECG will be received on cycle 1 day 10, in which the investigator should assess if the ASP2215 dose modification should occur as per the dose interruption or reduction guideline in Section 5.1.2 of the protocol.
- t. Thyroid function tests will be repeated after every 2 cycles of therapy (C3D1, C5D1, C7D1, etc.).

Table 2 Schedule of Assessments for Chemotherapy Arm

	Screening		Cv	cle 1		Cvo	ele 2	Subsequent Cycles
Activity	(Day -14		Day 4	Day 8	Day 15	Day 1	Day 15	Day 1
	to -1)	Day 1	± 1	± 1	± 1	± 2	± 1	± 2
Signed ICF	X							
Medical and Disease History	X							
Randomization		X^p						
Physical Examination ^b	X	Xa	X	X	X	X	X	X
Vital Signs	X	Xa	X	X	X	X	X	X
ECOG Performance	X	Xa			X	X	X	X
Prior and Concomitant Medications	X ^c	X	X	X	X	X	X	X
Pregnancy Test for Woman of Childbearing Potential	X ^d	X				X		X
Chest X-ray (or CT of chest) ^o	X							
12-lead ECG ^e	Xg	X			X	X		X

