Clinical Laboratory Tests (chemistry, hematology, coagulation, urinalysis) ^f	X ^g	Xa	Xa	Xa	Xa	Xa	Xa	Xa
Thyroid Function Tests	X							Xs
Coagulation Profile (PT/INR, D-dimer, fibrinogen)	X							
MUGA or ECHO ^h	X							
Ophthalmologic Assessment	Xi					X^{i}		X^{i}
FLT3 Mutation Status ⁱ (bone marrow aspirate or whole blood)	X							
Bone Marrow Aspiration and/or Biopsy	X^k				X^k	X^k		X^k
AE/SAE Assessment	X	X	X	X	X	X	X	X
PGx ¹		X						
Patient Reported Outcome Tools ^{q, r}		X ^a		X^q	X^q	X	X^q	X
EQ-5D 5L ^r		Xa				X		X
Resource Utilization		Xa				X		X
IRT Transaction Required ^p	X	X				X		X
LoDAC or Azacitidine Dosing					See Footnot	e ^m		
MEC or FLAG-IDA Dosing				See Fo	otnote ⁿ			

AE: adverse event; CR: complete remission; CRc: composite complete remission; CRi: complete remission with incomplete hematologic recovery; CRp: complete remission with incomplete platelet recovery; CT: computed tomography; ECG: electrocardiogram; ECHO: echocardiogram; ECOG: Eastern Cooperative Oncology Group; EDTA: ethylenediaminetetraacetic acid; EQ-5D-5L: EuroQol Group-5 Dimension-5 Level Instrument; FLAG-IDA: fludarabine, cytarabine and granulocyte colony-stimulating factor with idarubicin; FLT3: FMS-like tyrosine kinase; ICF: Informed Consent Form; INR: international normalization ratio; IRT: interactive response technology; LoDAC: low-dose cytarabine; MEC: mitoxantrone, etoposide and intermediate-dose cytarabine; MUGA: multigated acquisition scan; PGx: pharmacogenomics; PT: prothrombin time; SAE: serious adverse event *Footnotes continued on next page*

- Obtained predose.
- b. Height measurement performed only at screening. Weight measurement should be performed at screening and day 1 of each cycle.
- c. Includes medications taken within 28 days prior to cycle 1 day 1.
- d. Woman of childbearing potential must have a negative serum or urine pregnancy test (minimum sensitivity 25 IU/L or equivalent units of human chorionic gonadotropin) within 72 hours prior to the start of study treatment.
- e. Screening ECG is required. ECG assessment will be evaluated at predose of cycle 1 day 1, cycle 1 day 15 and day 1 each subsequent cycle. Predose assessments should be taken within 1 hour before drug administration. The 12-lead ECGs will be recorded in triplicate (3 separate ECGs 10 minutes resting prior to first ECG and at least 5 minutes apart per time point) and transmitted electronically for central reading. See Section 7.5.5 of the protocol.

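### The by-arm count of subjects with maximum QTcF above 480 ms is taken over unequal ECG schedules, so it is expected to run higher for ASP2215 even with no QT difference

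*SAP*

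**What the plan says.** Section 7.5.4 averages the three centrally read values at each time point and tabulates QTcF categories by arm and visit. It then adds a per-subject summary, the "Number and percent of subjects with maximum postbaseline QTcF > 480 msec", together with the time to that maximum, both by treatment group. It sets no common set of visits, no common time window and no adjustment for time on treatment.

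The schedules in Section 2 differ between arms:

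- **ASP2215 (Table 1, footnote e):** ECGs are "evaluated at predose of cycle 1 day 1, cycle 1 day 8, cycle 1 day 15 and day 1 of each subsequent cycle". Footnote s adds a conditional reading: "A confirmatory ECG should be performed on cycle 1 day 9 if the mean QTcF from cycle 1 day 1" to day 8 has risen by more than 30 ms with no other known cause.
- **Chemotherapy (Table 2, footnote e):** ECGs are "evaluated at predose of cycle 1 day 1, cycle 1 day 15 and day 1 each subsequent cycle". There is no day 8 or day 9 ECG.
- **Both arms (Table 3):** one ECG at the pre-HSCT or end-of-treatment visit.

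Treatment length differs too. MEC and FLAG-IDA are limited to two cycles (Table 2, footnote n). ASP2215, LoDAC and azacitidine continue until a discontinuation criterion is met (Section 3.2.1).

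The end-of-study analysis covers safety data (Section 1), and Section 7.5.4 is not excluded from it.

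**The concern.** The larger the number of readings a maximum is taken over, the more likely it is to exceed a fixed limit. ASP2215 subjects have at least one more scheduled post-baseline ECG at equal treatment length. Against MEC and FLAG-IDA they can also go on collecting ECGs after the comparator has stopped.

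QT prolongation is a listed adverse event of interest (Appendix 3), so the two percentages will be read side by side. Part of any excess for ASP2215 would reflect the number of looks, and the row does not let the reader separate that part from a drug effect.

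The time to maximum is not comparable for the same reason. Day 8 allows an earlier time for ASP2215 and longer treatment allows a later one. The direction is therefore not fixed, and its size was not calculated.

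**Working it through.** The SAP states no figure for this summary, so there is none to reproduce. The check asks what the row would show if QTcF behaved identically in both arms.

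**Model.** QTcF at a visit = subject mean + independent visit error. Subject means are normal with mean μ and SD s_b; visit errors are normal with SD s_w. The SAP gives none of these, so they are assumed: μ = 420 or 435 ms, and s_b/s_w = 15/8, 20/12 or 20/18 ms. The within-subject correlation, s_b²/(s_b² + s_w²), is then 225/289 = 0.78, 400/544 = 0.74 or 400/724 = 0.55. The probability of a maximum above 480 ms was simulated with 300,000 subjects per setting.

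Check on one reading: for μ = 435 and 20/12, P = 1 − Φ((480 − 435)/√544) = 1 − Φ(1.93) = 2.7%. The simulation gave 2.69%.

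**Post-baseline ECGs counted**

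- Chemotherapy, two-cycle course: cycle 1 day 15, cycle 2 day 1, end of treatment (3).
- ASP2215, same duration: these plus day 8 (4), and day 9 if day 8 minus day 1 exceeds 30 ms.
- ASP2215, four cycles: also day 1 of cycles 3 and 4 (6, plus any day 9).

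**Expected percentage with maximum above 480 ms, no QT difference**

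| μ, s_b/s_w | Chemotherapy | ASP2215, same duration (ratio) | ASP2215, 4 cycles (ratio) |
|---|---|---|---|
| 420, 15/8 | 0.06 | 0.07 (1.2) | 0.09 (1.5) |
| 420, 20/12 | 1.19 | 1.46 (1.2) | 1.92 (1.6) |
| 420, 20/18 | 3.28 | 4.14 (1.3) | 5.53 (1.7) |
| 435, 15/8 | 0.92 | 1.11 (1.2) | 1.45 (1.6) |
| 435, 20/12 | 5.64 | 6.66 (1.2) | 8.22 (1.5) |
| 435, 20/18 | 10.81 | 13.18 (1.2) | 16.88 (1.6) |

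**Day 9.** With no QT effect the trigger fires in 0.4% to 11.9% of subjects. Removing day 9 changes the same-duration figure by at most 13.18 − 13.05 = 0.13 percentage point. Day 8 and treatment length drive the excess.

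**Restriction to shared visits.** Over cycle 1 day 15 and cycle 2 day 1, if both are attended equally, the expected percentage is the same in both arms (for example 0.89% at 420, 20/12 and 4.40% at 435, 20/12). If the arms reach cycle 2 at different rates, some imbalance returns. With a proportion π reaching it, the count is π × P(two looks) + (1 − π) × P(one look). At an assumed 90% v 60%, with 435 and 20/12:

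- ASP2215: 0.9 × 4.40 + 0.1 × 2.69 = 4.23%
- Chemotherapy: 0.6 × 4.40 + 0.4 × 2.69 = 3.72%
- Ratio: 4.23/3.72 = 1.14

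The numbers with one and with two ECGs therefore need to be shown.

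**The case against.** **The by-visit table already answers the question.** Section 7.5.4 gives QTcF categories by arm at each visit, so the proportions above 480 ms at cycle 1 day 15 and cycle 2 day 1 will exist. This stands in part: a fair comparison at each shared visit is available. It does not correct the maximum-based count or the time to maximum, and nothing tells the reader which figures to compare.

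**The row is descriptive.** No test is planned, and the SAP also summarises extreme values by arm for liver tests and vital signs. That is true, and it limits the importance of the point. The row is still a by-arm percentage with a foreseeable tilt.

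**Adverse events are adjusted for exposure.** Section 7.5.1 gives events per patient-year. That addresses treatment length for coded QT events, but not the ECG count or the frequency of ECGs.

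**Stronger readings to avoid**

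- A reader might infer a two- to threefold excess. Treating readings as independent, with an assumed 1% chance per ECG, 1 − (1 − 0.01)^n gives 2.0% to 3.0% for 2 to 3 ECGs and 5.9% to 6.8% for 6 to 7, a ratio of 2.3 to 3. Readings in one subject are correlated, and allowing for that brings the four-cycle ratio down to 1.5 to 1.7.
- A reader might infer that ASP2215 has more cycles than the whole control arm by design. That holds only against MEC and FLAG-IDA. LoDAC and azacitidine are open-ended too, and the pooled-arm ratio depends on the regimen mix and time on treatment.
- A reader might infer that the triggered day 9 ECG is a main source of bias. With no QT effect it adds almost nothing.

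**Conclusion.** The point holds as a minor one. The unequal schedules and the unadjusted maximum are both in the SAP, and together they are expected to raise the ASP2215 percentage when QTcF does not differ. Under the assumed means and SDs the ratio is about 1.2 to 1.3 from the cycle 1 extras at equal duration, almost all of it from day 8. It is about 1.5 to 1.7 for four cycles of ASP2215 against a two-cycle chemotherapy course. In absolute terms the four-cycle excess runs from 0.03 to about 6 percentage points (0.09 − 0.06 and 16.88 − 10.81), so it is negligible where crossings are very rare.

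This is an expectation, not a prediction of the observed table. It overstates rather than hides a QT signal for ASP2215, and it says nothing about whether a true effect exists.

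**What to change.** In Section 7.5.4, state that the between-arm comparison of QTcF above 480 ms rests on look-matched figures:

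1. the by-visit proportions at cycle 1 day 15 and cycle 2 day 1, which are already planned; and
2. a per-subject count over those two visits, leaving out days 8 and 9, with the number of subjects who have one and two ECGs shown for each arm.

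Keep the all-ECG maximum and the time to maximum as within-arm descriptions, so that days 8 and 9 and later cycles stay visible. No ECG schedule or management rule changes.

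The cost is a subset of an existing table and one sentence of text. The downside is that the comparative count ignores later-cycle ECGs, which the all-ECG row still shows. Cycle 2 day 1 also includes only subjects who reach it, so the comparison there is not fully protected by randomisation.
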